6.2.4 Clinical Laboratory Parameters

Based on the safety population, continuous laboratory results will be summarized by visit, treatment group, and pooled BMS-986036. Categorical results such as those for urinalysis will be summarized by number and percentage of participants in each category. These summaries will be based on central laboratory results, except in rare circumstances in which only a local lab value is available then a local lab value may be used. This value will be presented in the same unit and summarized with the central results from other participants. Summaries will present both actual and change-from-baseline results for continuous values.

Sponsor: Bristol-Myers Squibb

Protocol no: MB130-068

The participants with abnormal post-baseline values of laboratory parameters (with available threshold values) will be descriptively summarized by counts and percentages by time point.

Laboratory values below the lower limit or above the upper limit of quantification will be imputed to the lower or upper limit, respectively, for summary tables. The actual values will be displayed in the listings.

Box plots will be presented by time point. All laboratory data specified in the summary tables will be present in listings.

6.2.5 Bone Mineral Density Testing (BMD)

BMD data will be summarized by visit, treatment group, and pooled BMS-986036. In rare circumstances where the number of evaluable lumbar spine segments changes over time for bone mineral density results, only participants with the same number and same segments as their baseline assessment will be included in change from baseline summaries of lumbar spine values. In addition, only participants with at least 2 evaluable lumbar spine segments at baseline will be included in the summary of the baseline time point. All bone mineral density results will be listed. Once available, the quality control (QC)-corrected values of BMD and t- and z-scores will be analyzed.

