Dispense study medication	X	X	X	X			See Section 8.4
Study medication return/reconcile		X	X	X	X	X	See Section 8.4

Table 3 Long-Term Bone Mineral Density and Immunogenicity Follow-Up Period Activities – Study MB130-068

Procedure/Assessment	6 Months After Week 52/PTFU (± 14 days) ^a	9 Months After Week 52/PTFU (± 14 days) ^b	12 Months After Week 52/PTFU (± 14 days) ^b	14 Months After Week 52/PTFU (± 14 days) ^b	Notes: 1 month is defined as 4 calendar weeks.
Concomitant medications since last visit	X				Selected medications that could impact bone mineral density assessment and nonalcoholic steatohepatitis (NASH) therapies taken after the end of study treatment will be recorded on the electronic case report form (eCRF) (Section 8.4.8)
Dual energy X ray absorptiometry (DXA)	X				See Section 8.5.3.8 . For participants who prematurely discontinue study medication, the follow up DXA scan is not required unless the participant has completed at least Week 16
Anti drug and anti FGF21 antibodies	X	X	X	X	See Section 8.5.3.6 and Appendix 10
Blood chemistry				X	See Section 8.5.3.6
Hemoglobin A1c				X	See Section 8.5.3.6
Serum for disease, target and drug effect biomarkers	X				See Section 8.5.4 and Table 8 . Participants should fast for at least 8 hours prior to the sample collection
Plasma for disease, target and drug effect biomarkers	X				See Section 8.5.4 and Table 8 . Participants should fast for at least 8 hours prior to the sample collection

^a Month 6 samples will be collected from all participants.

^b Performed only in participants for whom Long Term Immunogenicity Follow Up Visits are required.

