7.3 Safety Objective

To demonstrate the safety of BMS-986036 in adults with NASH and stage 3 liver fibrosis throughout the course of the study, including BMD and immunogenicity.

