8.3.7 Concomitant Medication Restrictions

Anti-diabetic, anti-obesity, and anti-dyslipidemic medications are allowed if participants have been on stable dosing regimens for at least 3 months (12 weeks) (6 weeks for statins) prior to and during the Screening Period. The investigator may contact the medical monitor regarding the stability of a participant's regimen when determining eligibility for study participation.

During study treatment, participants should refrain from using cannabinoid products.

[figure not shown]
Vitamin E is allowed; however, vitamin E doses ≥ 800 IU/day are allowed only if participants have been on stable doses for at least 6 months (26 weeks) prior to and during the Screening Period and if vitamin E treatment (≥ 800 IU/day) was not initiated after the qualifying liver biopsy was performed.

Vitamin D and calcium supplementation are permitted per local standard of care. Use of bisphosphonates, selective estrogen receptor modulators, estrogen, or teriparatide for treatment of osteoporosis is permitted if participants have been on stable doses for at least 6 months (26 weeks) prior to and during the Screening Period.

Any change in dose of these medications should be recorded in the electronic case report form (eCRF). Consult with the medical monitor if medications which could impact bone density assessments are to be added during the Double-Blind Treatment Period or during the first 6 months after the Week 52 / PTFU Visit.

Medical or surgical treatments for obesity should not be initiated while the participant is participating in the first 52 weeks of the study (i.e., from the time of informed consent until the participant completes the Week 52/PTFU Visit or discontinues participation in the study, whichever comes first).

Concomitant medications and medical and surgical treatments will not be limited after the Week 52/PTFU Visit.

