8.3.9 Withdrawal of Participants

8.3.9.1 Discontinuation of Study Medication

Participants MUST discontinue investigational product (IP) (and non-investigational product [non-IP] at the discretion of the investigator) for any of the following reasons.

- Participant's request to stop study medication. Participants who request to discontinue study medication will be expected to complete an ET Visit and subsequent follow-up visits/procedures per the Schedule of Activities (e.g., Week 52/PTFU; Section 1). The only exception to this is when a participant specifically withdraws consent for any further contact with him/her or persons previously authorized by participant to provide this information. Participants' withdrawal of consent should be explained in detail in the medical records by the investigator as to whether the withdrawal is from further treatment with study medication only or also from study procedures and/or ET, Week 52/PTFU Visit, etc. (see [Section 8.3.9.2](#))
- Any clinical AE, laboratory abnormality or intercurrent illness, which, in the opinion of the investigator, indicates that continued participation in the study is not in the best interest of the participant
- The participant experiences a major bone fracture or is diagnosed with osteoporosis that requires treatment
- Abnormal liver tests as defined in [Section 8.5.3.1](#)
- On 2 consecutive visits (at least 2 weeks apart), a participant has an eGFR < 30 mL/min/1.73 m², according to the *Modification of Diet in Renal Disease Study* equation
- If there is a significant protocol violation. The violation should be discussed with the medical monitor prior to discontinuing study medication
- Loss of ability to freely provide consent through imprisonment or involuntary incarceration for treatment of either a psychiatric or physical (e.g., infectious disease)

illness (Note: Under specific circumstances, a participant who has been imprisoned may be permitted to continue as a participant. Strict conditions apply, and sponsor approval is required.)

- The participant becomes pregnant (study medication must be discontinued immediately)

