4.3.6 Bone Mineral Density Testing (BMD)

BMD as measured by DXA at Week 48 (or ET, if applicable), and 6 months (1 month is defined as 4 calendar weeks) after the Week 52/PTFU Visit, following will be summarized.

- Absolute and change from baseline values

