5.0 Analysis Populations

- Enrolled Population: All participants who sign informed consent.
- Randomized Population: All participants who are randomized, analyzed as per randomized treatment.
- Modified intent-to-treat (mITT) Population: All participants who are randomized and receive at least 1 dose of study treatment, analyzed according to randomized treatment. All primary efficacy analyses will be conducted using this population.
- As Treated (Safety) Population: All participants who are randomized and receive at least 1 dose of study medication, analyzed according to treatment actually received. This population will be essentially the same as the mITT unless a participant received an incorrect treatment, i.e., a treatment different from what he/she was randomized to. All safety analyses will be conducted using this population.

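### The 6-month follow-up BMD summary takes no account of bone-active drugs started during the trial, so it could partly overstate recovery after stopping study drug

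*SAP*

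**What the plan says.** BMD is part of the safety objective in Protocol 7.3, which covers safety "throughout the course of the study, including BMD and immunogenicity". Protocol 8.5.3.8 schedules DXA at Screening, at Week 48 (or ET) and 6 months after Week 52/PTFU, a month being 4 weeks.

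SAP 4.3.6 asks for "Absolute and change from baseline values", and SAP 6.2.5 adds that "BMD data will be summarized by visit, treatment group, and pooled BMS-986036". The population is the As Treated set, of which SAP 5.0 says "All safety analyses will be conducted using this population". The restrictions in SAP 6.2.5 concern spine segments: where the evaluable segments differ over time, "only participants with the same number and same segments as their baseline assessment will be included in change from baseline summaries of lumbar spine", and the baseline summary needs at least two evaluable segments. Medication is not mentioned.

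On bone-active drugs:

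- Protocol 8.3.9.1 lists as a reason to stop study drug: "The participant experiences a major bone fracture or is diagnosed with osteoporosis that requires treatment". The same section expects those who stop to attend ET, PTFU and the later DXA visit. Protocol 8.5.3.8 limits the ET and follow-up scans to those who completed Week 16.
- Protocol 8.3.7 says "Concomitant medications and medical and surgical treatments will not be limited after the Week 52/PTFU Visit". It also asks for consultation with the medical monitor before a drug that could affect bone density is added, both on treatment and in the first 6 months after Week 52/PTFU.
- Protocol Table 3 provides that "Selected medications that could impact bone mineral density assessment and nonalcoholic steatohepatitis (NASH) therapies taken after the end of study treatment will be recorded", and Protocol 8.4.8 repeats this.
- SAP 6.5.6.2 presents these drugs in their own table and in a listing. Nothing links them to the BMD summary.

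**The concern.** The follow-up scan is this trial's evidence on whether any bone loss during 48 weeks of dosing persists or reverses. Starting a bone-active drug is plausibly driven by BMD itself, because the participants most likely to be treated are those who lost most. Protocol 8.5.1.1 and 8.5.1.3 withhold on-treatment biopsy and imaging results from sites; Protocol 8.5.3.8 says nothing similar about DXA.

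If study drug lowers BMD, treatment starts could be commoner in the active arms. The gain from that treatment then enters the active-arm follow-up mean and looks like recovery after stopping study drug. Comparison with placebo protects the reading only if start rates are similar across arms, which is what would fail if the drug has an effect. The protocol collects the information needed to deal with this, and the SAP does not use it.

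**Working it through.** The documents give no BMD effect, standard deviation, margin or expected number of treatment starts, so there is no stated figure to reproduce. All values of p, g and L below are assumptions.

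**1. Is there time for treatment to act before the scan?** The follow-up DXA comes 6 × 4 = 24 weeks after Week 52/PTFU, so 4 + 24 = 28 weeks after Week 48 (window ±14 days). The interval is the same after an ET visit, since PTFU follows ET by 4 weeks.

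**2. Shift in an arm's follow-up mean.** Let p be the share of the arm treated and g their gain, in percentage points of baseline BMD. Shift = p × g.

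- Low end: 0.02 × 2 = 0.04 points.
- High end: 0.10 × 5 = 0.5 points.

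In counts, using the approximately 49 per arm in Protocol 6.2 and g = 4:

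- 1 starter gives 4 × 1/49 = 0.08 points.
- 5 starters give 4 × 5/49 = 0.41 points.
- In the pooled active column (197 × 3/4 ≈ 148), 5 starters give 4 × 5/148 = 0.14 points.

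**3. Apparent recovery when there is none.** Let L be the mean loss at Week 48, the same for everyone, with no true recovery. Follow-up mean = −L + p × g, and apparent recovery = p × g / L. With L = 2, g = 4 and p = 0.10, the mean is −2 + 0.4 = −1.6, and apparent recovery is 0.4/2 = 20%. Over L = 1–3, g = 2–6 and p = 5–20%, the result runs from 0.05 × 2/3 = 3% to 0.20 × 6/1 = 120%. The inputs therefore decide the size. Complete masking needs p = L/g, which is 50% at L = 2 and g = 4.

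**4. Does dropping the treated scans solve it?** Suppose 10% of an arm lost 5 points and were then treated, gaining 4. The other 90% lost 1 point, and nobody truly recovered.

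| Summary | Week 48 | 6 months | Apparent recovery |
|---|---|---|---|
| As planned | 0.1(−5) + 0.9(−1) = −1.4 | 0.1(−1) + 0.9(−1) = −1.0 | 0.4 |
| Post-treatment scans dropped, by visit | −1.4 | −1.0 | 0.4 |
| Same untreated participants at both visits | −1.0 | −1.0 | 0 |

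Dropping scans visit by visit leaves the false recovery unchanged, because the largest losers count at Week 48 and vanish at follow-up. With a gain of 2 it does worse: the planned follow-up mean is 0.1(−3) + 0.9(−1) = −1.2, against −1.0 after exclusion. Using the same untreated participants at both visits removes the artefact, but it does not show the 5-point losers. They have to be reported beside it.

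**The case against.** The strongest case against is that the plan already shows most of what matters, and that the effect is hypothetical and probably small.

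- All BMD results and all medications are listed by participant, post-treatment bone drugs are tabulated by arm, and osteoporosis, osteopenia and fractures are events of special interest. This stands: loss in an individual is not concealed. A reconstruction from listings is, however, post hoc.
- A reader might infer from the sentence on treatment after Week 52/PTFU that bone drugs are then uncontrolled. Protocol 8.3.7 does not support that, since it asks for consultation through the first 6 months afterwards. Consultation is not a prohibition, so new treatment before the scan remains possible.
- The on-treatment route is narrow. Protocol 8.3.2 excludes a T-score of −2.5 or less from age 40, and between Screening and Week 48 the only study DXA is at ET. This limits the likely numbers.
- Protocol 6.3.2.4 reports no meaningful mean BMD difference at end of dosing or 6 months later, though after only 12 or 16 weeks of dosing. Protocol 6.1.1 attributes the animal bone effects to weight loss and slower growth except at the highest monkey dose. Both lower the prior concern; neither covers 48 weeks.
- The table is descriptive, with no test or margin, and the SAP plans no reversibility claim. That limits the stakes, but the follow-up scan invites that reading.

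**Conclusion.** The point holds as an omission. SAP 6.2.5 includes by default every follow-up scan in the As Treated set and does not use the medication data collected because those drugs could affect that scan. If study drug lowers BMD and treatment starts are therefore commoner in active arms, the follow-up mean could partly overstate recovery. The size is unknown: 0.04 to 0.5 points in an arm mean with 2–10% treated and a gain of 2–5 points, and less in the pooled active column for the same number of starters.

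Two stronger readings go too far. A reader might infer that the plan hides bone loss on study drug. It does not: loss at Week 48/ET stays visible for drugs started later, every result is listed, and with few starters the effect is partial attenuation. A reader might also take the word for pooling in SAP 6.2.5 to mean that bone-treated and untreated participants are deliberately combined. It refers to the three dose arms. The change is worth making because it is cheap and concerns a named safety objective.

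**What to change.** Keep the planned table and add to SAP 6.2.5:

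1. The within-participant BMD change from Week 48/ET to the 6-month DXA, by arm. Restrict it to participants with both scans who did not start or increase a bone-active drug after Day 1 and before the follow-up scan. Use the same participants at both visits, and define the drugs by the list selected for the eCRF.
2. By arm, the number excluded for such a drug, with their last BMD change from baseline before it was started and their change at follow-up. Where the drug began before any post-baseline DXA, state that no pre-treatment change is available.

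Read any statement on reversibility from both versions side by side. The exclusion version should not stand alone, because it may leave out those with the largest loss.

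The cost is SAP wording and one extra descriptive table, with slightly fewer participants, from data already collected. Trial conduct and clinical management are unaffected.

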6.2 Study Rationale

The current study is designed to confirm and extend the results observed in the Phase 1 and 2a studies with BMS-986036. Specifically, this study aims to demonstrate in participants with NASH and stage 3 liver fibrosis, the efficacy of BMS-986036 using histological and noninvasive endpoints, and the safety of BMS-986036 as assessed by AEs, lab results and bone mineral density (BMD) monitoring.

The protocol was planned to randomize approximately 160 participants to 1 of 4 treatment groups (approximately 40 participants per group). This protocol amendment (Version 4.0) reflects that, upon close of enrollment, 197 participants were randomized to treatment (approximately 49 participants per group). The increased number of randomized participants occurred following: 1) unexpectedly high enrollment rate in the

final month of the enrollment period and 2) an unexpected decrease in the actual screen failure rate for subjects entered in the final month of enrollment.

Based on the unmet medical need for patients, the benefit/risk assessment discussed in [Section 6.3](#), and the strict safety monitoring of all participants, the potential clinical benefit outweighs the risks for those who have chosen to participate in this study. No additional revisions are required in [Section 9](#) due to the increased number of randomized participants.

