6.3.2.4 Effects on Bone

In the multiple ascending dose portion of Study MB130001, conducted in healthy participants, all dose panels had a decrease in bone formation markers (bone-specific alkaline phosphatase [BSAP] and N-terminal propeptide- of type 1 procollagen [P1NP]) that was reversible after administration of BMS-986036 had ended. The bone marker values remained within the normal reference range in all participants, and the percent decrease from Baseline did not differ between treated participants and the pooled placebo group. Similarly, there was no significant change in bone resorption markers in any BMS-986036-treated participants compared to the pooled placebo group.

Analyses from Phase 2 studies (MB130002 and MB130045) in participants with T2DM and in participants with NASH suggest that BMD, as measured by bone densitometry, was not affected by 12 or 16 weeks of dosing with BMS-986036. There were no meaningful differences in population mean BMD change from Baseline at the end of dosing or at 6-months follow-up.

Additionally, in both studies, BMS-986036 had no clinically meaningful impact on biomarkers of bone turnover (BSAP, P1NP, or C-terminal telopeptides type I collagen [CTX-1]) during 12 or 16 weeks of treatment.

Overall, the results from Phase 1 and Phase 2a studies have demonstrated that BMS-986036 was clinically well tolerated in obese participants, in obese participants with T2DM, and in participants with NASH with stage 1-3 liver fibrosis and has an acceptable safety profile to support continued clinical development.

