9.5.3 Safety Analyses

Safety analyses will be performed using the As Treated population. For analysis, all treatment-emergent (i.e., occurring after the first dose of study medication) AEs, SAEs, and AEs of special interest will be summarized by system organ class, preferred term, and treatment. Vital signs, immunogenicity, BMD, and laboratory data will be summarized by treatment. ECG abnormalities, physical examination abnormalities, if present, will be summarized.

Responses of anti-BMS-986036 antibodies and anti-FGF21 antibodies will be listed and tabulated by treatment and study day. The relationship between immunogenicity and PK and/or PD may be explored.

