3.3 Safety Objectives

The safety objectives of this study are to demonstrate the safety of BMS-986036 in adults with NASH and stage 3 liver fibrosis throughout the course of the study, including bone mineral density and immunogenicity.

Sponsor: Bristol-Myers Squibb

Protocol no: MB130-068

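### The objective is to demonstrate safety including bone density, but no BMD difference from placebo, confidence interval or margin is planned

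*SAP*

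**What the plan says.** Protocol 7.3 gives the safety objective as "To demonstrate the safety of BMS-986036 in adults with NASH and stage 3 liver fibrosis throughout the course of the study, including BMD" and immunogenicity. SAP 3.3 repeats it: "to demonstrate the safety of BMS-986036 in adults with NASH and stage 3 liver fibrosis", again naming bone mineral density.

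The analysis is set out in three places:

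- Protocol 9.5.3: "Vital signs, immunogenicity, BMD, and laboratory data will be summarized by treatment".
- SAP 4.3.6, for Week 48 (or early termination) and for six months after the Week 52 visit: "Absolute and change from baseline values".
- SAP 6.2.5: "BMD data will be summarized by visit, treatment group, and pooled BMS-986036". It adds rules for evaluable lumbar segments and says that QC-corrected BMD and t- and z-scores will be analysed, without naming a method.

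Nothing elsewhere supplies a comparison. SAP 6.5 specifies n, mean, SD, quartiles and range for continuous data. The ANCOVA and repeated-measures models in SAP 6.4 are for exploratory endpoints, and SAP 4.5 does not list BMD among them. By contrast, SAP 6.1.1 plans 95% intervals for each dose against placebo on the primary efficacy endpoint.

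**The concern.** An objective to demonstrate safety implies evidence that harm beyond some size has been ruled out. Descriptive summaries by arm do not report such evidence. A reader told that mean BMD changes looked alike would not learn from the planned output how large a loss on drug remains compatible with the data.

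Bone is a named risk here. Protocol 6.1.1 reports decreases in bone mass, mineralization and strength in animals. These were attributed to weight loss and slower growth except at the highest monkey dose, which was at 19 times the AUC. Bone-related events are of special interest (Protocol 8.5.3.7), and a further DXA is scheduled six months after Week 52. On the 12- and 16-week studies, Protocol 6.3.2.4 concludes: "There were no meaningful differences in population mean BMD change from Baseline at the end of dosing or at 6-months follow-up". The present trial treats for 48 weeks, and Protocol 6.2.1 says its safety results will feed Phase 3 design and dose selection. The size of bone loss not excluded, for each dose, is a figure that decision would need.

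**Working it through.** **The plan's own figure.** There is none for BMD: no SD, margin, power or precision is stated. The only power statement (Protocol 9.1, at least 80%) concerns the histology endpoint. It reproduces as a lower bound (about 86% to 87% by normal approximation at 40 per arm, one-sided 0.05) but has no bearing on BMD.

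**Inputs.**

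- 197 randomised 1:1:1:1 (Protocol 6.2 and 8.1): 197/4 = 49.25, so about 49 per arm and 3 × 49 = 147 on pooled drug.
- Missing scans: no rate is given. As an assumption, 15% missing gives 49 × 0.85 ≈ 42 per arm and 126 pooled.
- SD of BMD change: not given, so results are first stated in SD units.

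**Unadjusted 95% half-width for drug minus placebo,** in SD units: h = t(0.975, df) × √(1/n₁ + 1/n₀).

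- One dose, 49 v 49: 1.985 × √(2/49) = 1.985 × 0.2020 = 0.40
- Pooled, 147 v 49: 1.972 × √(1/147 + 1/49) = 1.972 × 0.1650 = 0.33
- One dose, 42 v 42: 1.989 × √(2/42) = 1.989 × 0.2182 = 0.43
- Pooled, 126 v 42: 1.974 × √(1/126 + 1/42) = 1.974 × 0.1782 = 0.35

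If the observed difference were exactly zero, the limit on the side of loss would lie at these values. Adjustment for baseline may narrow them somewhat.

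**In percentage points,** for an assumed SD of percent change from 2% to 5% (not a document figure), 49 per arm:

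| Assumed SD | Half-width, one dose | Half-width, pooled |
|---|---|---|
| 2% | 0.80 | 0.65 |
| 3% | 1.20 | 0.98 |
| 4% | 1.60 | 1.30 |
| 5% | 2.01 | 1.63 |

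**Is the trial too small to see a difference?** Approximate power of a two-sided 5% comparison of one dose with placebo is Φ(Δ/SE − 1.96), where SE = SD × 0.2020. For Δ = 2 points and SD 3%, SE = 0.606 and Φ(3.30 − 1.96) = 91%. For Δ = 1 point and SD 3%, Φ(1.65 − 1.96) = 38%. Over assumed SDs of 2% to 5%, power is 70% down to 17% for 1 point, above 99% down to 51% for 2 points, and above 99% down to 84% for 3 points. The answer depends on two quantities that the documents do not give: the SD and the difference of interest.

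**The case against.** Descriptive safety summaries are usual in Phase 2, and nowhere does the plan say that similar arm means will be taken as proof of no effect. BMD means are not the only bone evidence: bone-related adverse events including fractures, t- and z-scores and a pooled-drug summary are planned, and a data monitoring committee reviews safety. Because SAP 6.5 reports n, mean and SD, a reader can construct an interval from the output.

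All of this stands, and it rules out several stronger readings that a reader might infer:

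- *The arms are too small to show bone loss.* Not established. Without an SD or a difference of interest, limited size is shown only for small differences or a large SD.
- *A bone conclusion can rest only on similar-looking BMD means.* Not so, given the other bone data. Those data do not, however, bound the BMD difference from placebo.
- *No bound can be obtained.* A crude unadjusted one can. What is missing is a prespecified, displayed and baseline-adjusted one.
- *The earlier studies were analysed in the same way.* Protocol 6.3.2.4 gives their conclusion and does not describe the method.

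None of these removes the mismatch between an objective to demonstrate and an analysis that reports no comparison with placebo. If precision turns out to be good, showing the interval would help the sponsor.

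**Conclusion.** The concern holds as a gap between objective and analysis. BMD is named in an objective to demonstrate safety, yet no difference from placebo, interval or margin is planned for it. The reported results will therefore not say what size of loss is excluded.

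The half-widths above measure the gap: a modest loss would remain unexcluded for any single dose even with identical observed means. These figures assume that all 49 per arm, or 42 after an assumed 15% loss, have evaluable scans, that the SD is common to the arms, and that there is no covariate adjustment. Whether a loss of that size matters clinically cannot be judged from the documents, and this point does not claim that the trial is inadequate in size for bone.

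**What to change.** In SAP 6.2.5, for each DXA site (femoral neck, total hip, lumbar spine):

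1. Fit an ANCOVA of BMD change from baseline at Week 48, and another at the 6-month follow-up, in the safety population, with treatment, baseline BMD and the five randomisation strata as terms. Keep the existing lumbar-segment rule.
2. Report each dose minus placebo and pooled drug minus placebo with two-sided 95% confidence intervals. Name the Week 48 contrasts as the main ones; with three sites and two time points there are 4 × 3 × 2 = 24 intervals, of which 12 are at Week 48.
3. State how early-termination scans are handled, since SAP 4.3.6 places them with Week 48 and Protocol 8.5.3.8 allows them once the Week 16 visit is complete. Either summarise them separately or include them only in a stated sensitivity analysis.
4. State that the bone conclusion is read from the confidence limit on the side of loss, and that similar means or an interval containing zero do not show absence of effect.

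In Protocol 7.3 and SAP 3.3, replace *demonstrate* with *assess*, because no margin is set. Align the safety wording in the design statements (Protocol 6.2, 6.2.1 and 8.1, SAP 2.1).

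The cost is SAP and protocol wording and one extra table per site, from scans already scheduled. The intervals will be wide and unadjusted for multiplicity, and the bone-safety claim becomes more modest.
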